Primary End Point	To evaluate the safety of the DIALIVE in patients with Acute on chronic liver failure (ACLF)	The percentage of subjects who experience at least one (1) serious adverse event (SAE) between study Day 1 and Day 10; especially the incidence rate of SAE in both arms of the study at Day 1 and Day 10. The percentage of subjects who discontinued DIALIVE due to a serious adverse device event (SADE) between Day 1 (first day of treatment) and Day 10 (DIALIVE arm only).
Secondary End Point(s)	To evaluate the impact of biochemical performance outlined hereunder towards clinical benefit for patients receiving DIALIVE treatment plus Standard of Care vs Standard of Care alone	 Mortality: 28-days and 3 months Change in ACLF Grade Change in CLIF-ACLF score Improvement in individual organ function: brain (HE), kidney (serum creatinine), CVS (mean arterial pressure), pulmonary (P/F ratio or S/F if arterial blood gas info is not available), liver (serum bilirubin) and coagulation (INR and platelet levels). Status of ICU and Hospital Discharge (including discharge to a hospice for palliative care). Lengths of stay in ICU and hospital at D28 and D90. ICU and hospital re-admissions with another episode of ACLF up to 90 days post randomization.

Clinical Investigation Plan	CIP YAQ-002	Version: 7.0 10 October 2019
-----------------------------	-------------	------------------------------

Secondary end	Objectives	Outcomes Measures
Point(s)	To evaluate the performance of the DIALIVE in patients with ACLF	 Change in Plasma endotoxin level (endotoxin activity and endotoxin concentration) between; Study D1,D3, D5 and D10 across SOC arm
		2. Study D1, D3, D5 and D10 across DIALIVE arm
		Start and end of a treatment session with
		DIALIVE on D1, D2 and D3 4. Study D1, D3, D5 and D10 between SOC and DIALIVE arms for patients with the same grade of ACLF at the time of inclusion in the study
		Target-Value (TV): 40% reduction; Acceptable-Value (AV): 20% reduction Change in Albumin function (Human non- mercapt albumin -2 (HNA-2) / Human marcapt albumin (HMA) ratio:
		5. Study D1, D3, D5 and D10 across SOC arm6. Study D1, D3, D5 and D10 across DIALIVE
		arm 7. Start and end of a treatment session with DIALIVE on D1, D2 and D3.
		8. Study D1, D5 and D10 between SOC and DIALIVE arms for patients presenting with the same grades of ACLF
		TV: 40% reduction; AV: 20% reduction

Clinical Investigation Plan CIP YAQ-002 Version: 7.0 10 0	October 2019
---	--------------

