5.1 General

This is a European, multi-centre, randomised, controlled, study to generate data for the evaluation of safety (as measured by the percentage of subjects who experience at least one serious adverse event (SAE)) and performance (as measured by plasma endotoxin concentrations and albumin function) of the DIALIVE in 30 evaluable patients with Acute on Chronic Liver Failure (ACLF) versus standard of care (SOC). The study will therefore be open label. The design is appropriate for the study as the primary outcome is to assess safety of the device on a small group of patients.

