5.1.2 Primary Endpoints

The goal is to evaluate the percentage of subjects who experience at least one (1) serious adverse event (SAE) between study Day 1 and Day 10; especially the incidence rate of SAE between the study groups occurring in the period of Day 1 to Day 10.

The percentage of subjects who discontinued DIALIVE due to a serious adverse device event (SADE) between Day 1 (first day of treatment) and Day 10 (DIALIVE arm only)¹⁰.

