Adverse Event (AE)	Any untoward medical occurrence, unintended disease or injury, or untoward clinical signs (including abnormal laboratory findings) in subjects, users or other persons, whether or not related to the investigational medical device. Note 1: This definition includes events related to the investigational medical device or the comparator Note 2: This definition includes events related to the procedures involved Note 3: For users or other persons, this definition is restricted to events related to investigational medical devices
Adverse Device Effect (ADE)	Adverse Event related to the use of an investigational device. Note 1: This definition includes AEs resulting from insufficient or inadequate instructions for use, deployment, implantation, installation, or operation, or any malfunction of the investigational device Note 2: This definition includes any event resulting from use error or from intentional misuse of the investigational medical device
Serious Adverse Event (SAE)	 Any adverse event that: Led to death, injury or permanent impairment to a body structure or a body function Led to serious deterioration in the health of the subject, that either resulted in a life-threatening illness or injury, or a permanent impairment of a body structure or a body function, or in-patient or prolonged hospitialization, or in medical or surgical intervention to prevent life-threatening illness Led to foetal distress, foetal death or a congenital anomaly or birth defect Planned hospitalization for a pre-existing condition or a procedure required by the CIP, without a serious deterioration in health is NOT considered a SAE.
Serious Adverse Device Effect (SADE)	An ADE that has resulted in any of the consequences characteristic of an SAE
Unanticipated Serious Adverse Device Effect (USADE)	An SADE, which by its nature, incidence, severity or outcome has not been identified in the current version of the risk analysis report.
Device Deficiency (DD)	Inadequately of a medical device with respect to its identity, quality, durability, reliability, safety or performance. Note 1: this includes malfunctions, use errors, and inadequate labeling

An adverse event does not include:

Clinical Investigation Plan	CIP YAQ-002	Version: 7.0 10 October 2019
-----------------------------	-------------	------------------------------

- Medical or surgical procedures; the condition that leads to the procedure is an adverse event.

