- Pre-existing disease, conditions, or laboratory abnormalities present at the start of the study that do not worsen in frequency or intensity.
- Situations where an untoward medical occurrence has not occurred (e.g., hospitalizations for cosmetic or elective surgery or social/convenience admissions);
- The disease being studied or signs/symptoms associated with the disease unless more severe than expected for the subject's condition.
 - Expected post-operative course (see section 3)
- 12.2. Reporting requirements and timelines
- The SAE reporting form in appendix 1 of the MEDDEV guidance will be used unless national/local requirements specify a different reporting requirement.

In line with MEDDEV guidance 2.7/3 rev 3 May 2015 and Annex X section 2.3.5 of the MDD⁴⁰

Term	Reporter	Reported to	Reporting Timeline from awareness of the event
Adverse Event (AE)	Investigator	Sponsor/CRO	As soon as reasonably possible
Adverse Device Effect (ADE)	Investigator	Sponsor/CRO	As soon as reasonably possible
	Investigator	Sponsor/CRO	Immediately, not later than 3 calendar days after site awareness of event
Device Deficiency (DD)	Sponsor/CRO	CA/Ethics Committee	Immediately but no later than 2 calendar days if the event may have led to an SAE if; • suitable action had not taken • intervention had not been made • if circumstances had been less fortunate
	Investigator	Sponsor/CRO	Immediately, not later than 3 calendar days after site awareness of event
Serious Adverse Event (SAE), Serious Adverse Device Effect (SADE), Unanticipated Serious Adverse Device Effect (USADE)	Sponsor/CRO	CA/Ethics Committee	Immediately but not later than 2 calendar days of sponsor becoming aware of event if event indicates an imminent risk of death, serious injury, or serious illness and that requires prompt remedial action for other patients, users or persons, or a new finding to it For all other events Immediately but not later than 7 calendar days of sponsor becoming aware of event
New findings/updates in relation to already reported events	Sponsor/CRO	CA/Ethics Committee	Immediately but not later than 7 calendar days of sponsor becoming aware of event

 $^{^{\}rm 40}$ Special national requirements might apply and will be implemented

Clinical Investigation Plan CIP YAQ-002 Version: 7.0 10 October 20	19
--	----

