12.5. Foreseeable adverse events and anticipated adverse device effects

Listed below are known complications associated with liver disease

- Gastrointestinal bleeding
- Spontaneous Bacterial Peritonitis (SBP)
- Hepatic Encephalopathy (HE)
- Hypotension
- Septic shock
- Respiratory failure
- Cardiovascular failure
- Renal insufficiency
- Hepatorenal syndrome
- Death

Any existing condition will be recorded at baseline during screening. Further events relating to an existing condition will not be recorded as an AE unless in the opinion of the PI, the condition has worsened since baseline. All AEs will be recorded from the point of consent and reported to the Sponsor in accordance with section 13.2.

During initial human dialysis sessions, and subsequent DSMB reviews, the following (potential) device related SAEs were observed; these were incorporated in the latest version of the Investigator Brochure:

- Hypotension: this resulted in a series of recommendations to follow during the DIALIVE treatment (see §3.2 of CIP)
- Higher then expected albumin drop during dialysis led to additional in vitro tests supporting the need to administer
 g albumin every hour of dialysis (see §3.4 of CIP and §8.1 of IB)
- Anemia was observed in one patient, requiring blood cell pack administration to restore the hemoglobin level. (see page §3.2 of CIP and §9.1, 11.2 and 12.3i of IB)

Reference is made to section 3.2 of this document, where also the anticipated events related to extracorporeal circulation and to kidney dialysis are summarized

Clinical Investigation Plan CIP YAQ-002 Version: 7.0 10 0	October 2019
---	--------------

12.6. Emergency contact details for reporting serious adverse events, serious adverse device effects and device deficiencies.

All SAEs and USADEs will be reported to the CRO via the eCRF. In the event access to the eCRF is not available, paper SAE forms will be completed by the site and emailed to:

[contact]

or via fax ([contact]).

Please refer to Appendix 6 for Country Specific Safety Reporting.

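### Two rules in section 12 decide differently whether expected, non-fatal worsening of ACLF is an adverse event, so an unblinded investigator can count it in the primary SAE percentage or leave it out

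*Protocol*

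**What the plan says.** The first primary endpoint (section 5.1.2 and the synopsis) is "the percentage of subjects who experience at least one (1) serious adverse event (SAE) between study Day 1 and Day 10", with emphasis on comparing the arms.

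Section 12.1 defines an SAE as "Any adverse event that: Led to death, injury or permanent impairment to a body structure or a body function", followed by further seriousness criteria. An event must be an adverse event before it can be a serious one.

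Three statements then govern disease-related events:

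- **Section 12.1, list of what an adverse event does not include, pre-existing disease:** "Pre-existing disease, conditions, or laboratory abnormalities present at the start of the study that do not worsen in frequency or intensity".
- **Same list, studied disease:** "The disease being studied or signs/symptoms associated with the disease unless more severe than expected for the subject's condition".
- **Section 12.5, where the comparison is with the baseline state:** "Further events relating to an existing condition will not be recorded as an AE unless in the opinion of the PI, the condition has worsened".

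Section 12.5 also has a list introduced by "Listed below are known complications associated with liver disease". It includes encephalopathy, hypotension, septic shock, and respiratory, cardiovascular and renal deterioration, and it stands under a heading on foreseeable adverse events. Sections 12.3.3 and 12.3.4 use the protocol as the reference for classing disease-related events as expected or unexpected.

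Section 5.1 states: "The study will therefore be open label". Section 12.3 has the site investigator assess each adverse event. Section 12.4.1 makes every death during participation an SAE.

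**The concern.** ACLF often progresses. Section 2.7 cites 28-day mortality of 22%, 32% and 78% for grades 1, 2 and 3. A rule that drops disease signs unless they exceed what is expected can therefore remove much of what happens to these patients, whereas a rule based on worsening from baseline keeps it. The protocol contains both and does not say which prevails.

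The choice falls to someone who knows the arm, and patients are not watched equally. Those on DIALIVE are treated in an ICU or similar setting with an arterial line and two-hourly blood gases during sessions (section 2.2). SOC patients may be on a general ward (synopsis). Hypotension is both a listed disease complication and a potential device-related SAE already observed (section 12.5). It can be recorded as a possible device effect in one arm and passed over as the course of the disease in the other. A device effect can equally be put down to the disease.

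At stake are the between-arm SAE percentage and the cohort-by-cohort comparison of adverse events on which the DSMB decides about continuation (section 5.3.7).

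**Working it through.** The plan states no figure that bears on this point. The main check is a comparison of the rules, followed by what little arithmetic the document allows.

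**1. The rules side by side.** Take a patient whose ACLF worsens from baseline without dying, in a way the investigator regards as expected for that patient.

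| Rule | Test applied | Adverse event? |
|---|---|---|
| 12.1, pre-existing disease | Has it worsened? | Not excluded |
| 12.1, studied disease | Is it worse than expected? | Excluded |
| 12.5 | Has it worsened since baseline, in the investigator's opinion? | Recorded |

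ACLF is both the pre-existing disease and the studied disease, so all three rules apply and the answers differ. If the event also meets a seriousness criterion of 12.1, the patient is in the primary numerator under the first and third rules and out of it under the second, unless another SAE already counts.

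**2. How the rest of section 12 uses expectedness.** Sections 12.3.3 and 12.3.4 treat it as a label attached to an event already recorded. The studied-disease bullet uses it to decide whether the event is recorded at all.

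**3. Effect of one patient.** Section 5.2 gives 5 cohorts of 3 DIALIVE and 3 SOC evaluable patients: 5 × 3 = 15 per arm, 30 in all, which agrees with section 5.3.7.

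- Whole arm, evaluable patients: 1/15 = 6.7 percentage points per reclassified patient.
- One cohort, evaluable patients: 1/3 = 33 points.
- Main analysis: section 6 uses the safety population, and evaluable patients serve the sensitivity analysis. Appendix 7 reports 8 DIALIVE patients enrolled for 6 evaluable. If that ratio held (an assumption), 15 × 8/6 = 20 patients, and one patient moves the DIALIVE arm by 1/20 = 5.0 points.

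**4. Illustration only.** Let p be the share with serious non-fatal disease worsening in Days 1 to 10, q the share with an SAE that always counts, independent of the former, and a the fraction of p that is recorded. The recorded SAE share is

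1 − (1 − p·a)(1 − q),

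and with equal true rates the spurious difference between arms is p(1 − q)(a₁ − a₂). None of p, q or a is in the document. Assuming p of 20–60%, q of 0–20%, full recording in one arm and half in the other:

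- lowest: 0.20 × 0.80 × 0.5 = 8 points;
- highest: 0.60 × 1.00 × 0.5 = 30 points.

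If the fraction recorded is the same in both arms, the difference is 0, whichever rule is used. The level still changes: at p = 40% and q = 10%, it is 46% in each arm with all worsening recorded and 10% with none.

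**The case against.** The strongest reply is that section 12 can be read consistently. If what is expected is taken to mean the patient's recorded baseline condition, the studied-disease bullet says the same as its neighbour. The list of foreseeable events and the expectedness category both presume that disease events are recorded. That reading is reasonable, but the bullet does not tie expectation to baseline, and a site that takes it at face value follows the text.

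The second reply is that there are safeguards. The trial management group is consulted on adjudication (section 7.1.4), monitors check adverse event recording (section 5.5), the DSMB reviews safety data, and ACLF grade and organ function are secondary endpoints. These make deterioration visible elsewhere. They do not repair the primary endpoint: the group includes site investigators, no blinding is stated for it, and an event never recorded as an adverse event need not reach it or the DSMB.

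Three stronger readings should be resisted:

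- **That 12.5 captures any worsening automatically.** It does not; it too rests on the investigator's opinion. Removing the other bullet narrows discretion without ending it.
- **That a move from grade 1 to grade 2 with new renal failure on, say, Day 4 is an SAE under 12.5 and no event under 12.1.** Neither follows. It is an SAE only if it meets a seriousness criterion, and many investigators would call it worse than expected, so it could count under 12.1 as well.
- **That the bias is 20 or 30 points, or favours a known arm.** Such sizes come from assumed inputs, and the direction could go either way.

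**Conclusion.** The concern holds in this form: the protocol gives conflicting rules on whether expected, non-fatal worsening of the studied disease is an adverse event, and the conflict reaches the primary endpoint because SAEs are a subset of adverse events. A difference in its application between arms is possible, given open-label assessment and unequal monitoring, but the document does not show that it occurs.

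Only the per-patient effect can be derived: about 6.7 points at 15 evaluable per arm, and less in a larger safety population. The 8 to 30 points above rest wholly on assumed rates and recording fractions. No test, alpha or power is affected, since the study is descriptive (section 4.2). The percentages are themselves the primary result, so their definition needs to be unambiguous.

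**What to change.** In section 12.1, delete the studied-disease bullet, or limit it to signs and symptoms unchanged from baseline. State one rule for both arms, in 12.1 and 12.5 alike: any new or worsened condition relative to the recorded baseline is an adverse event and is then assessed for seriousness under 12.1, whether or not it was expected. Keep expectedness for the field in 12.3.4.

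If CLIF-C OF or ACLF grade is used as an objective cross-check, limit it to the visits common to both arms within the endpoint window: Days 1, 3, 5 and 10. The DIALIVE schedule has a Day 2 visit that SOC lacks (section 5.4), so scoring every visit would give that arm more chances to register a worsening. Apply the cross-check to cohorts already enrolled as a sensitivity check. It has limits: visit scores cannot recover events between visits, and the kidney score uses creatinine or renal replacement (Appendix 1b), which the dialysis component of DIALIVE may influence (section 2.2).

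**Cost.** Protocol wording and a note to sites; no new assessments. More disease-related adverse events and SAEs will be recorded in both arms. Patients enrolled before the change were recorded under the present wording. This version is dated October 2019 and section 5.3.8 expects recruitment to run to December 2019, so results before and after the change should be distinguishable in the report.

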12.3. Assessments of adverse events

Each adverse event will be assessed by the PI for the following criteria:

12.3.1. Severity

Category	Definition
Mild	The adverse event does not interfere with the volunteer's daily routine, and does not require intervention; it causes slight discomfort
Moderate	The adverse event interferes with some aspects of the volunteer's routine, or requires intervention, but is not damaging to health; it causes moderate discomfort
Severe	The adverse event results in alteration, discomfort or disability which is clearly damaging to health Note: A severity rating of severe does not necessarily categorise the event as an SAE.

12.3.2. Seriousness

Seriousness as defined for an SAE in section 13.1.

12.3.3. Causality

The relationship between the use of DIALIVE treatment and the occurrence of each adverse event shall be assessed and categorised. During causality assessment activity, clinical judgment shall be used and the relevant documents, (IB and the CIP) shall be consulted, as all the foreseeable serious adverse device effects (SADE) and the potential risks are listed and assessed there. The presence of confounding factors, such as concomitant medication/treatment, the natural history of the underlying disease, other concurrent illness or risk factors shall also be considered. For the purposes of this investigation the device related expected events will be outlined in the IB, The CIP will outline the disease expected events and cross refer to the IB.

The above considerations apply also to the serious adverse effects (SAEs) occurring in the comparison group.

For the purpose of harmonising reports, each SAE will be classified according to five different levels of causality. The Sponsor and the investigators will use the following criteria to assess the relationship of the serious adverse event to the investigational medical device or procedures.

Not related Relationship to the device or procedures can be excluded when:

- the event is not a known side effect of the product category the device belongs to or of similar devices and procedures;
- the event has no temporal relationship with the use of the investigational device or the procedures;
- the serious event does not follow a known response pattern to the medical device (if the response pattern is previously known) and is biologically implausible;
- the discontinuation of medical device application or the reduction of the level of activation/exposure when clinically feasible and reintroduction of its use (or increase of the level of activation/exposure), do not impact on the serious event;
- the event involves a body-site or an organ not expected to be affected by the device or

procedure;

- the serious event can be attributed to another cause (e.g. an underlying or concurrent illness/clinical condition, an effect of another device, drug, treatment or other risk factors);
- the event does not depend on a false result given by the investigational device used for diagnosis when applicable;
- harms to the subject are not clearly due to use error;
- In order to establish the non-relatedness, not all the criteria listed above might be met at the same time, depending on the type of device/procedures and the serious event.

Unlikely

The relationship with the use of the device seems not relevant and/or the event can be reasonably explained by another cause, but additional information may be obtained.

Possible

The relationship with the use of the investigational device is weak but cannot be ruled out completely. Alternative causes are also possible (e.g. an underlying or concurrent illness/ clinical condition or/and an effect of another device, drug or treatment). Cases were relatedness cannot be assessed or no information has been obtained should also be classified as possible.

Probable

The relationship with the use of the investigational device seems relevant and/or the event cannot reasonably explained by another cause, but additional information may be obtained.

Causal relationship

The serious event is associated with the investigational device or with procedures beyond reasonable doubt when:

- the event is a known side effect of the product category the device belongs to or of similar devices and procedures;
- the event has a temporal relationship with investigational device use/application or procedures;
- the event involves a body-site or organ that o the investigational device or procedures are applied to; o the investigational device or procedures have an effect on;
- the serious event follows a known response pattern to the medical device (if the response pattern is previously known);
- the discontinuation of medical device application (or reduction of the level of activation/exposure) and reintroduction of its use (or increase of the level of activation/exposure), impact on the serious event (when clinically feasible);
- other possible causes (e.g. an underlying or concurrent illness/ clinical condition or/and an effect of another device, drug or treatment) have been adequately ruled out;
- harm to the subject is due to error in use;
- the event depends on a false result given by the investigational device used for diagnosis when applicable;
- In order to establish the relatedness, not all the criteria listed above might be met at the same time, depending on the type of device/procedures and the serious event.

The sponsor and the investigators will distinguish between the Serious Adverse Device Effects (SADEs) related to DIALIVE treatment and those related to investigation procedures (any procedure specific to the clinical investigation). An adverse event can be related both to procedures (inherent in the study) and the investigational device. Complications of procedures are considered not related if the said procedures would have been applied to the patients also in the absence of investigational device use/application.

Particular attention shall be given to the causality evaluation of unanticipated serious adverse (device) events (USADEs). The occurrence of unanticipated events related to the use of DIALIVE could suggest that the clinical investigation places subjects at increased risk of harm than was to be expected beforehand. The DSMB will review all

Clinical Investigation Plan CIP YAQ-002 Version: 7.0 10 October 2019
--

safety data at specific time points throughout the study as outlined in the DSMB charter.

